6.10.2 Assessment of Steady-State Achievement

Assessment of time to achieve steady-state for the 3 treatments will be performed by a review of weekly donepezil trough levels (C_{tau}).

In the current study, TDS C_{tau} levels of interest are the plasma concentrations measured immediately prior to TDS removal on Days 8, 15, 22, 29, and 36. For Aricept, C_{tau} levels of interest are the plasma concentrations measured immediately prior to dosing on Days 8, 15, 22, 29, and 36 following dosing in each period (i.e., Study Days 8, 15, 22, 29, and 36 in Period 1, Study Days 44, 51, 58, 65, 72 in Period 2, and Study Days 80, 87, 94, 101, and 108 in Period 3).

Separate mixed effect models will be used to assess the steady-state of each treatment with consideration of potentially significant sequence effect on Treatments B and C due to lack of washout between periods. For Treatment A the mixed effect model will include Day (Days 8, 15, 22, 29, and 36) as the fixed effect and subject as the random effect. For Treatments B and C two mixed effect models will be used to assess the steady-state:

1. Assess the steady-state of each treatment by period (i.e. Treatment B in Period 2, Treatment B in Period 3, Treatment C in Period 2, and Treatment C in Period 3 using a mixed effect model with Day (Days 8, 15, 22, 29, and 36 in periods 2 or 3) as the fixed effect and subject as the random effect.

Page 27 of 61 Confidential

2. Assess the steady-state of each treatment combining both periods using a mixed effect model with Day (Days 8, 15, 22, 29, and 36) and sequence as the fixed effects and subject as the random effect.

The least squares means (LSMs) of the log-transformed C_{tau} (pre-dose concentrations) for Treatments A through C will be estimated from the mixed-effect models with Day being treated as a repeated measure within a subject. An unstructured covariance structure will initially be used. If problems with convergence arise, an AR(1) covariance structure will be used.

The C_{tau} concentrations observed on Day 15 through Day 36 will be compared with the average C_{tau} levels for the rest of the period to determine the time at which steady state was achieved. The following orthogonal Helmert transformation contrasts that compare each day (8, 15, 22, 29 and 36) to the mean C_{tau} concentrations over all subsequent time points will be tested for each treatment group:

- Day 8 C_{tau} value vs. the average of Day 15 through Day 36: C'1 = (1, -1/4, -1/4, -1/4, -1/4)
- Day 15 C_{tau} value vs. the average of Day 22 through Day 36: C'2 = (0, 1, -1/3, -1/3, -1/3)
- Day 22 C_{tau} value vs. the average of Day 29 through 36: C'3 = (0, 0, 1, -1/2, -1/2)
- Day 29 C_{tau} value vs. Day 36: C'4 = (0, 0, 0, 1, -1)

Testing of the contrasts will proceed in the order shown. The first non-significant comparison (p >0.05) will be interpreted as the day (8, 15, 22, or 29) at which steady-state concentrations were attained.

The LS mean estimate associated with the contrasts and their corresponding 90% confidence intervals, the p-value for the difference of the least squares means (LSMs) (In transformed scale), and the geometric mean ratios and their 90% confidence intervals will be provided for each treatment group. The LSM estimates and CI limits for the natural log values will be exponentiated. For the geometric mean ratio and its CI limits, the natural log values will be exponentiated and multiplied by 100.

Example SAS code for the steady-state assessment of Treatment A in Period 1 or Treatments B or C in a specific period:

Page 28 of 61 Confidential

Where		

Example SAS code for the steady-state assessment of Treatments B or C with data from both Period 2 and Period 3:

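### As worded, the steady-state models in SAP 6.10.2 add a redundant random subject effect to an unstructured covariance, and the equal-variance AR(1) fallback has no defined trigger

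*SAP*

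**What the plan says.** SAP 6.10.2 models log trough concentrations on five days per period.

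- **Random part.** For Treatment A, and for Treatments B and C by period, the model has "Day (Days 8, 15, 22, 29, and 36) as the fixed effect and subject as the random effect" (with small wording differences). The model that combines periods for B and C has Day "and sequence as the fixed effects and subject as the random effect".
- **Repeated part.** The least squares means are "estimated from the mixed-effect models with Day being treated as a repeated measure within a subject".
- **Covariance.** "An unstructured covariance structure will initially be used. If problems with convergence arise, an AR(1) covariance structure will be used".
- **Decision rule.** Four contrasts are tested in order, each day against the mean of the later days. The second is "Day 15 C_{tau} value vs. the average of Day 22 through Day 36: C'2 = (0, 1, -1/3, -1/3, -1/3"). Then: "The first non-significant comparison (p >0.05) will be interpreted as the day (8, 15, 22, or 29) at which steady-state concentrations were attained".

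The section does not define a convergence problem, does not say whether the random subject effect stays under AR(1), and names no degrees-of-freedom method. Two blocks of example SAS code are announced, but their content is not visible in the public copy. The post-lock addendum's list of changed sections does not include 6.10.2.

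**The concern.** Two descriptions of within-subject correlation are placed in one model. A random subject effect adds the same covariance to every pair of days. An unstructured matrix already lets every pair have any covariance. Together they have no unique solution, so a numerical warning may come from the specification and not from the data.

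That matters because the only remedy named is AR(1), which assumes equal variance on all five days. In Period 1 this is doubtful: subjects start without donepezil, so Day 8 troughs also carry differences between subjects in half-life, and these fade by later weeks. The reported day is the first contrast with p > 0.05, so the standard errors decide it. The choice of covariance should not rest on an undefined warning or be made after the data are seen.

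At stake is the day reported in Tables 14.4.26 and 14.4.27, which supports describing Week 5 as steady state.

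**Working it through.** The plan gives no figure for this analysis, so there is none to reproduce.

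**1. Parameter count.** Five days give 5 × 6 / 2 = 15 distinct variances and covariances. Unstructured (UN) uses all 15; the subject variance σ²b makes 16. The total covariance is V = σ²b·J + R, with J a matrix of ones and R unstructured. For any small enough σ²b, R = V − σ²b·J gives the same V. The Jacobian of this map has 16 columns and rank 15.

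**2. Effect on the UN fit.** On one simulated data set, σ²b was set to 0, 0.0174, 0.0348 and 0.0627, with R absorbing the rest. The −2 restricted log-likelihood was −685.650 each time, and the standard errors of the four contrasts were 0.0202, 0.0187, 0.0205 and 0.0250 each time. The redundancy does not bias the UN contrasts; it only makes the fit numerically ill-defined.

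**3. Expected troughs.** The protocol's clinical overview gives a half-life of about 70 h. Starting from zero, the fraction of steady state after t hours is 1 − 2^(−t/70):

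- Days 8, 15, 22, 29, 36: 81.1%, 96.4%, 99.3%, 99.9%, 100.0%.
- Log-scale contrasts 1 to 4: −0.199, −0.034, −0.006, −0.001.

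**4. Is equal variance plausible in Period 1?** The derivative of ln(1 − e^(−kt)) with respect to ln k is kt·e^(−kt)/(1 − e^(−kt)). If half-life has a CV of 30% (an assumption), between-subject differences in half-life add SDs of about 0.104, 0.033, 0.009 and 0.002 to contrasts 1 to 4. Homogeneous AR(1) cannot represent that pattern; UN can.

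**5. Does the dated day change?** 400 simulated data sets per scenario, complete data, sequential contrasts at 0.05. Treatment A uses n = 55, the number SAP 6.12 expects for adhesion. Assumed, because the documents do not give them: between-subject SD 0.3, and the log-SD of the elimination rate k and the residual SD shown below (base case 0.3 and 0.12). Degrees of freedom, also assumed: n − 1 for UN and 4(n − 1) for the AR(1) models. RI means random subject effect.

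| Scenario | Dated by the day shown: UN / RI + AR(1) / AR(1) alone | RI + AR(1) against UN: earlier / later |
|---|---|---|
| A, base case | Day 15: 42 / 45 / 73% | 4.75 / 1.75% |
| A, SD of k 0.2, residual 0.20 | Day 15: 76 / 78 / 92% | 2.25 / 0.5% |
| A, SD of k 0.4, residual 0.10 | Day 15: 16 / 23 / 47% | 12.75 / 0.25% |
| A, Day 8 residual 0.35 | Day 15: 44 / 84 / 92% | 41.5 / 2.5% |
| A, SD of k 0.15, residual rising 0.08 to 0.25 | Day 15: 56 / 78 / 93% | 21.75 / 0.25% |
| A, Days 8 and 15 residual 0.25, others 0.10 | Day 15: 77 / 64 / 83% | 1.25 / 13.5% |
| A, equal variances, true AR(1) errors | Day 15: 57 / 54 / 76% | 1 / 4% |
| B, Period 2 from half level, n = 25 | Day 8: 9 / 7 / 34% | 2 / 4% |
| B, Period 3, already flat | Day 8: 94 / 94 / 99% | 1.75 / 1.25% |

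In the base case, median standard errors of RI + AR(1) relative to UN were 0.88, 1.07, 1.08 and 1.03 for contrasts 1 to 4. With AR(1) alone, rejection of contrast 2 fell from 57% to 26% and of contrast 3 from 6% to 1%, while contrast 4, which compares adjacent assessment days, stayed at 5%. That fits a correlation forced to decay with distance, which inflates contrasts spanning several days. It also occurs under equal variances, so the equal-variance assumption is not the only cause.

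**6. Sensitivity to degrees of freedom.** A second set of 300 data sets per scenario used n − 1 for both models, n = 55, between-subject SD 0.35, half-life CV 30/40/50% and within-subject SD 0.15/0.12/0.10. UN and RI + AR(1) dated different days in 6/12/15% of data sets, with AR(1) earlier in 5/11/15%. For Treatment B in Period 2 (n = 24, half-life CV 40%) 11% differed, in both directions.

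**The case against.** A reader might infer that the model must fail, that AR(1) will therefore be used, that steady state will be dated too early, and that the bioequivalence result is weakened. The documents do not support that chain.

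- **The fallback is conditional.** The redundant parameter leaves the likelihood, contrasts and standard errors unchanged. Software may stop normally, set the subject variance to zero, or only warn.
- **The code is not visible.** The prose could be a loose description of a single repeated statement with UN. The actual model may already be sound.
- **The direction is not fixed.** With the random effect kept, as the text literally has it, the shift is early in some scenarios and late in others. It depends on day-specific variances that the documents do not give.
- **The consequence is limited.** No rule links the dated day to the bioequivalence analysis; exposure is taken in Week 5 regardless (SAP 3.1, 6.2.11.2 and 6.10.3). At a 70 h half-life, Days 15 and 22 are both above 96% of steady state and both precede Week 5. The SAP also reports each contrast's geometric mean ratio with a 90% interval, and plots the troughs.

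All four points stand, and they limit the finding to a specification error in a supportive analysis. They do not remove it: the text as written is over-parameterised, and neither the trigger nor the form of the fallback is stated. The choice between one heterogeneous structure and another is partly preference.

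**Conclusion.** The model as worded is not identifiable: 16 covariance parameters, rank 15. This follows from the text and needs no assumption about the data. Numerical warnings are foreseeable but not certain, and the SAP does not say which of them leads to AR(1).

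If the fallback is used, the dated day can change. With the random effect kept, the base-case change was in 6.5% of runs (4.75 + 1.75), and across scenarios it went either way. With AR(1) replacing the random effect, a reading the SAP leaves open, the tilt was early in every scenario tried; in the base case the most frequent answer moved from Day 22 (54% under UN) to Day 15 (73%). These sizes rest on assumed variances and the 70 h half-life. The primary Week 5 comparison is unaffected. The correction should be made because it costs little and removes an avoidable reason for falling back.

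**What to change.** In SAP 6.10.2:

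1. Fit Day as a repeated measure within subject with an unstructured covariance and no random subject effect. Delete the random subject effect from these models.
2. Name Kenward-Roger degrees of freedom.
3. Make non-convergence of that model the only trigger for a fallback, and define it.
4. Replace homogeneous AR(1) with a heterogeneous-variance structure, for example ARH(1) or heterogeneous compound symmetry.
5. Make text and SAS code agree. If the code already omits the random effect, only the text needs changing.

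The cost is a few sentences of SAP wording and, if needed, a small edit to the model code; no new data. As an addendum dated after database lock already exists, record the change as post-lock and state which covariance model was actually fitted for each treatment and period.

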6.10.3 Statistical Assessment of Bioequivalence at Steady-State

To examine the relative bioavailability at steady state of the 5 and 10 mg/day TDS (Tests) relative to Aricept (Reference), plasma donepezil exposure as characterized by AUC_{0-168,ss} and C_{max,ss} will be assessed and compared utilizing bioequivalence criteria. The least squares geometric means (LSGM) of the PK parameters for each treatment will be reported. Point estimates and 90% Confidence Intervals (CI) for the Test to Reference ratios of geometric means will be provided. Similar bioavailability for donepezil will be concluded if the 90% CIs of the LSGMs lie within the acceptable range of 0.80 to 1.25 for AUC_{0-168,SS} and C_{max,ss} (C_{max,ss} for informational purposes). Forest plots presenting the point estimate and 90% confidence intervals for AUC_{0-168,ss} and C_{max,ss} will be constructed for the comparisons between the 5 mg/day and 10 mg/day donepezil TDS applications (Tests) and oral Aricept[®] (Reference).

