STATISTICAL ANALYSES	PharmacokineticsPlasma concentrations and PK parameters of donepezil and 6-O-desmethyl donepezil will be tabulated using summarystatistics.To examine the donepezil PK at steady state (Week 5 of 5 x1-week wear) after 5 and 10 mg/day TDS applicationcompared to oral Aricept ® , an analysis of variance (ANOVA)will be performed on the natural logarithms of AUC0-168,SSand C max . Dose-normalization will be applied as appropriate.Differences between each Test and Reference in the PKparameters will be tested at the 5% level of significance.
	Time to Steady State Assessment Assessment of time to achieve steady-state will be performed by a review of weekly donepezil trough levels (C tau ) at time points immediately prior to dosing on Days 15, 22, 29, and 36 in each treatment period. The univariate analysis method described by Chow and Liu for examining when steady-state is attained will be implemented using log-transformed trough plasma concentrations. Modifications to the method for Treatment Periods 2 and 3 will be explained in the Statistical Analysis Plan (SAP), to possibly adjust for the attainment of a new steady state after switching to a new treatment without a washout period after the previous treatment.
	Relative BioavailabilityTo examine the relative bioavailability at steady state of the5 and 10 mg/day TDS (Tests) relative to oral donepezil(Reference), plasma donepezil exposure as characterized byAUC 0-168 at steady state will be assessed and comparedutilizing bioequivalence criteria.Since the intention of the patch is to decrease the peak-to-

through fluctuations with lower $C_{max}$ after the patch application compared to daily oral Aricept dosing, rather than using the conventional bioequivalence criterion for $C_{max}$ , it is stipulated that mean steady-state donepezil $C_{max}$ after patch administration should remain between the steady-state $C_{max}$ and $C_{min}$ after daily oral Aricept ® administration.

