# 17.3.6. Statistical Assessment of Relative Bioavailability

To examine the relative bioavailability at steady state of the 5 and 10 mg/day TDS (Tests) relative to oral donepezil (Reference), plasma donepezil exposure as characterized by AUC0-168,SS will be assessed and compared utilizing bioequivalence criteria. The least squares geometric means (LSGM) of the PK parameters for each treatment will be reported. Point estimates and 90% Confidence Intervals (CI) for the Test to Reference ratios of geometric means will be provided. Similar bioavailability for donepezil will be concluded if the 90% CIs of the LSGMs lie within the acceptable range of 0.80 to 1.25 for AUC0-168,SS. Forest plots presenting the point estimate and 90% confidence intervals for AUC0-168,SS will be constructed for the comparisons between the 5 mg/day and 10 mg/day donepezil TDS applications (Tests) and oral Aricept® (Reference).

Since the intention of the patch is to decrease the peak-to-through fluctuations with lower Cmax after the patch application compared to daily oral Aricept dosing, rather than using the conventional bioequivalence criterion for  $C_{max}$ , it is stipulated that mean steady-state donepezil  $C_{max}$  after patch administration should remain between the steady-state  $C_{max}$  and  $C_{min}$  after daily oral Aricept® administration.

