3 ENDPOINTS

3.1 Primary Endpoints

Page 6 of 61 Confidential

• Primary pharmacokinetic parameters at steady state (Week 5) calculated for plasma concentrations of donepezil will include: AUC_{0-168,ss} and C_{max,ss}

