1. BACKGROUND

This document details changes and / or additions to the planned statistical analyses for Corium, Inc. protocol CL-P-20003, a study titled "A Phase 1, Open-Label, 3-Period, Randomized, Crossover Pharmacokinetic Study to Evaluate the Steady-State Pharmacokinetics of 5 mg and 10 mg Corplex[™] Donepezil Transdermal Delivery Systems Compared to 10 mg Oral Administration of Aricept® in Healthy Volunteers" previously described in V1.0 of the Statistical Analysis Plan (SAP) dated 9-MAR-2021.

1.1 Rationale for Addendum:

- i. Changes made to the SAP in Sections: 6.2.11.1, 6.10.1, 6.10.3, 6.11.1, and 6.12
- ii. To update the changes in title and numbering of three tables
- iii. To update the changes made to table, figure and listing shells

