2.3 Change 3 in Section 6.10.3

2.3.1 **Original text**

Since the intention of the patch is to decrease the peak-to-through fluctuations with lower Cmax after the patch application compared to daily oral Aricept dosing, rather than using the conventional bioequivalence criterion for Cmax, ss, it is stipulated that mean steady-state donepezil Cmax, ss after patch administration should remain between the steady-state Cmax,ss and Cmin,ss after daily oral Aricept® administration.

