2.3.2 New text

Original text removed.

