POST DATABASE LOCK STATISTICAL ANALYSIS PLAN ADDENDUM

Table 14.1.3.1	Added a footnote: Percentage for Fertility Status is calculated from the
	number of females
Table 14 3 2 1	Added footnotes: "Subjects are counted once within a system organ class
14010 11. 5.2.1	and once for each unique preferred term. Percentages are based on the
	number of subjects in the Safety Analysis Population by treatment and
	overall."
Table 14.3.5.1	Footnotes modified
Table 14.3.6.1	Table title and Visit label modifications
Table 14.3.7.12	Added footnote: "Due to a study administration error, only the 0.5-hour
	assessment was performed following removal of the Week 5 TDS for
	Treatments A and B."
Table 14.3.7.13	Added footnote: "Due to a study administration error, only the 0.5-hour
	assessment was performed following removal of the Week 5 TDS for
	Treatments A and B."
Table 14.3.7.14	Added footnote: "Due to a study administration error, only the 0.5-hour
	assessment was performed following removal of the Week 5 TDS for
	Treatments A and B."
Table 14.3.7.20	Renumber Table 14.6.1 to Table 14.3.7.20
Table 14.3.7.21	Renumber Table 14.6.2 to Table 14.3.7.21
Table 14.6.1	Removed
Table 14.6.2	Removed
Figure 14.4.3	Planned Figure:
	Mean Plasma Donepezil and 6-O-Desmethyl Donepezil Concentration-Time
	Data after 5 mg/day TDS Application on Week 5 (Days 29-36 Following
	TDS Application) on Linear Scale - PK Population
	Updated Figure:
	Mean Plasma 6-O-Desmethyl Donepezil to Donepezil Concentration Ratios
	after 5 mg/day TDS Application on Week 5 (Days 29-36 Following TDS
	Application) on Linear Scale - PK Population
Figure 14.4.4	Dlanned Figure
Figure 14.4.4	riameu riguie.

 QMD Ref: Worldwide-TMP-ST-008-2.0 Effective: 12Aug2019
 Governing QMD: Worldwide-SOP-ST-001

 Confidentiality Statement

 This document is the property of Worldwide Clinical Trials Inc. and may not be duplicated, copied, altered or removed from company without prior approval from Worldwide Quality Assurance or in compliance with Worldwide Standard Operating Procedures.

 DEF. W. H. J. J. TRICK ON 1001110

Worldwide Clinical Trials Controlled Quality Management Document

		WORLDWIDE	
--	--	-----------	--

Sponsor: Protocol Number: Corium, Inc. CL-P-20003

POST DATABASE LOCK STATISTICAL ANALYSIS PLAN ADDENDUM

	Mean Plasma Donepezil and 6-O-Desmethyl Donepezil Concentration-Time Data after 10 mg/day TDS Application on Week 5 (Days 29-36 Following
	IDS Application) on Linear Scale - PK Population
	Opdated Figure:

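### SAP 6.10.3 no longer contains the protocol's own criterion for Cmax, removed by a post-lock addendum, and SAP Section 7 wrongly reports no change from the protocol

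*SAP*

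**What the plan says.** **Protocol.** The synopsis and Section 17.3.6 judge AUC0-168,ss by a 90% confidence interval within 0.80 to 1.25. For Cmax they choose a different route, "rather than using the conventional bioequivalence criterion for" Cmax: because the patch is meant to flatten the profile, mean Cmax "after patch administration should remain between the steady-state" Cmax and Cmin on daily oral dosing.

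**Current SAP.** Section 3.1 introduces its list with "Primary pharmacokinetic parameters at steady state (Week 5) calculated for plasma concentrations of donepezil will include" and then names AUC0-168,ss and Cmax,ss. Section 6.10.3 concludes similar bioavailability if the 90% confidence intervals "lie within the acceptable range of 0.80 to 1.25 for AUC_{0-168,SS} and C_{max,ss} (C_{max,ss} for informational purposes"). It does not mention the range between oral Cmax and Cmin. Section 7, which is the place for departures from the protocol, reports none.

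**Addendum.** Under the heading "POST DATABASE LOCK STATISTICAL ANALYSIS PLAN ADDENDUM", Change 3 gives the former text of 6.10.3 ("it is stipulated that mean steady-state donepezil Cmax, ss after patch administration should remain between the steady-state Cmax,ss and Cmin,ss after daily oral" dosing) and then the new text: "Original text removed". No reason is shown. The stated scope is "Changes made to the SAP in Sections: 6.2.11.1, 6.10.1, 6.10.3, 6.11.1, and 6.12".

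**The concern.** Two things are wrong. First, the protocol fixed in advance how patch Cmax would be judged, and the SAP no longer reports that judgement. It puts Cmax,ss into the sentence that defines the bioequivalence conclusion, under limits the protocol had declined to use, and calls it informational there but primary in Section 3.1. A reader cannot tell what a Cmax result would mean. Second, Section 7 tells the reader that the analyses match the protocol. Anyone relying on it would not look for the Cmax change or for the changed ANOVA model.

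At stake is what the report says about Cmax and whether its account of protocol departures is accurate. The AUC conclusion is not at stake.

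**Working it through.** **1. The plan's own figure, and what it covers.** Protocol 17.2 claims at least 90% power with 48 completers, a true AUC ratio of 1.05, a CV of 29% and limits of 80 to 125%. For two one-sided 5% tests in a 2x2 crossover:

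- σ = √ln(1 + 0.29²) = 0.284
- SE = 0.284 × √(2/48) = 0.0580, with 46 degrees of freedom
- Power = 0.9045 (normal approximation 0.912). With 46 subjects it is 0.893.

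The figure reproduces. It concerns AUC only, so the Cmax point leaves the sample size untouched.

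**2. Can the two readings of Cmax disagree?** The documents give no Cmax ratio or CV, so this is illustrative. Assume 48 subjects and a CV of 29%. The last column is Φ(−ln(ratio)/0.0580). It covers the upper half of the protocol criterion only, on the ratio of geometric means.

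| True patch/oral Cmax ratio | P(90% CI within 0.80–1.25) | Same, CV 20–35% | P(estimated ratio below 1), CV 29% |
|---|---|---|---|
| 0.85 | 0.27 | 0.22–0.43 | 0.997 |
| 0.90 | 0.64 | 0.51–0.89 | 0.965 |
| 0.95 | 0.90 | 0.78–0.99 | 0.81 |

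A patch that lowers Cmax as intended could well fall outside 0.80–1.25 while staying below oral Cmax. The two criteria are not interchangeable.

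**3. Section 7 against the current texts.**

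| Item | Protocol | Current SAP | In addendum? | Weight |
|---|---|---|---|---|
| Cmax criterion | 17.3.6, synopsis: between oral Cmax and Cmin | 6.10.3: absent | Yes, Change 3 | Clear |
| ANOVA | 17.3.4: one 3-way model with sequence, period, treatment | 6.10.1: 2-way model for B vs C; A vs C model without period or sequence | No | Clear |
| Comparison population | 17.1: PK-PP, defined per treatment | 6.1.3: data needed on both B and C | No | Smaller: detailed PK-PP criteria are left to the SAP, but the B-and-C requirement is new |
| TEAE window | 17.6: to 5 days after last dose | 6.11.1: to follow-up visit | Yes, Change 4 | Smaller: see below |
| Trough days, Period 1 | 17.3.5: Days 15, 22, 29, 36 | 6.10.2: Day 8 added | No | Smaller: 17.3.5 leaves only Periods 2 and 3 to be modified |

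The follow-up visit is 5 ± 2 days after the last oral dose or TDS removal, so it falls on day 3 to day 7. Counting a patch dose to its removal, the two windows differ by at most about 2 days.

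That makes five departures. Two are logged in the addendum and 5 − 2 = 3 are not; Section 7 lists none. The addendum names SAP 6.10.1, but its change there is an intraclass-correlation formula, not the ANOVA model. Section 7 is not among its five sections.

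**4. Dates.** SAP Section 1 also relies on a protocol clarification memo of 30 October 2020, which is not available. SAP V1.0 is dated 9 March 2021 and, by the addendum's account, still held the Cmax criterion. The memo therefore cannot explain that deletion. It could bear on the unlogged items.

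**The case against.** The deletion is open: the addendum prints the removed text. Marking Cmax,ss as informational is in keeping with the protocol's refusal of the conventional limits. The protocol says what should hold but not what follows if it does not. The Cmax,ss ratio and interval are still reported, and Tables 14.4.12, 14.4.14 and 14.4.16 summarise patch and oral parameters, so a careful reader could check the criterion unaided. All of this stands, and it limits the weight of the point. It does not make Section 7 accurate, and it does not supply the judgement that the protocol promised.

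A reader might also count every mismatch between the two documents as an undeclared departure. Two do not qualify:

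- **C-SSRS.** The synopsis promises a summary table and SAP 6.11.6 gives a listing. But Protocol 17.6 allows additional safety parameters to be given in data listings, so the inconsistency lies inside the protocol.
- **Adhesion by week.** Protocol 17.4 asks for summaries by week, and SAP 6.12 mentions only summaries by treatment. SAP 6.3 refers layout to the table shells, which are not available, so omission is not shown.

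**Conclusion.** Section 7 is wrong as written, and SAP 6.10.3 fails to carry the protocol's Cmax criterion. Two departures are clear (Cmax criterion, ANOVA model) and three are smaller. This should be corrected, but it is not a threat to the trial's main conclusion.

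A reader might infer that the criterion was removed because of the results. The documents do not support that: they give the timing by the addendum's heading and no reason, and they do not say what data had been seen. Nor do they show that the unlogged departures were made after lock. A reader might also infer that bioequivalence is in doubt; the AUC0-168,ss conclusion and the power are unaffected.

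The finding rests on comparing current protocol text with current SAP text. For the unlogged items it assumes that the unseen memo did not authorise them. The probabilities for Cmax rest on assumed ratios and CVs and show only that the two criteria can differ.

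**What to change.** **SAP 6.10.3.** Report the protocol criterion as met or not met: mean patch Cmax,ss against mean oral Cmax,ss and mean oral Cmin,ss. Do this for 10 mg/day, and for 5 mg/day after dose-normalisation (×2, Protocol 17.3.2). Use the arithmetic mean, which is what Protocol 17.3.2 and SAP 6.3 mean by the term, show geometric means as supportive, and state which subjects contribute. Name only AUC0-168,ss in the 0.80–1.25 conclusion sentence. Keep the Cmax,ss ratio and its 90% confidence interval as descriptive results.

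**SAP Section 7.** List the actual departures. For those made after database lock, give the date, the reason and what data had been seen. If the sponsor keeps the deletion, still report the protocol criterion and record its removal here.

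**Cost.** One small output not now in the SAP Section 9 list, plus wording. Cmax,ss and Cmin,ss are already derived (SAP 6.2.11.2), and both kinds of mean are already standard summaries (SAP 6.3). The downside for the sponsor is that the result is reported whichever way it falls, and that changes made after lock are disclosed.
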